7.2.5 Sponsor Responsibility for Reporting Adverse Events

All Adverse Events will be reported to regulatory authorities, IRB/IECs and investigators in accordance with all applicable global laws and regulations.

7.3 TRIAL GOVERNANCE AND OVERSIGHT

7.3.1 Scientific Advisory Committee

This trial was developed in collaboration with a Scientific Advisory Committee (SAC). The SAC comprises both Sponsor and non-Sponsor scientific experts who provide input with respect to trial design, interpretation of trial results and subsequent peer-reviewed scientific publications.

8.0 STATISTICAL ANALYSIS PLAN

This section outlines the statistical analysis strategy and procedures for the study. If, after the study has begun, but prior to any unblinding, changes are made to primary and/or key secondary hypotheses, or the statistical methods related to those hypotheses, then the protocol will be amended (consistent with ICH Guideline E-9). Changes to exploratory or other non-confirmatory analyses made after the protocol has been finalized, along with an explanation as to when and why they occurred, will be listed in the Clinical Study Report (CSR) for the study. Post hoc exploratory analyses will be clearly identified in the CSR. No separate Statistical Analysis Plan (SAP) will be issued for this study.

8.1 Statistical Analysis Plan Summary

This section contains a brief summary of the statistical analyses for this trial. Full detail is in the Statistical Analysis Plan (SAP) (Section 8.2).

8.1.1 Efficacy Analysis

This study will randomize approximately 54 subjects in a 2:1 ratio into 2 treatment groups (Group 1: IMI/REL and Group 2: CMS + IMI) in order to obtain a minimum of 45 subjects (15 per infection type) who meet the criteria for inclusion in the microbiological modified intent-to-treat (mMITT) population.

The mMITT population is defined as all randomized subjects who receive at least one dose of each study drug within a given IV study therapy regimen, and who have a baseline bacterial pathogen meeting inclusion criterion #3; in the case of a polymicrobial infection, at least one pathogen must satisfy the requirements of inclusion criterion #3, and all pathogens identified at the baseline time point must be susceptible to both IMI/REL and colistin. An additional 5 to 10 subjects with imipenem-resistant and colistin-resistant bacterial infection will be enrolled into a third non-randomized, open-label treatment group (Group 3: IMI/REL). The analysis and summarization of the efficacy data will be limited to point estimates and summary statistics such as 95% confidence intervals. No inferential testing between the treatment groups will be performed.

The primary objective of the study is to estimate the proportion of subjects with a favorable overall response within each of the randomized treatment groups (Group 1: IMI/REL and

Group 2: CMS + IMI). This primary estimation will incorporate data from three different subgroups of subjects defined by infection site (HABP/VABP, cIAI, and cUTI). Within each infection type, favorable overall response is defined differently and this information will be pooled to provide an estimate of favorable overall response. In addition, an estimate of favorable response within each of Treatment Group 1 (IMI/REL) and Treatment Group 2 (CMS + IMI) will be provided for each infection type. Favorable overall response will be estimated based on the following: (a) survival status (based upon all-cause mortality) through Day 28 post-randomization in subjects with HABP/VABP, (b) clinical response at Day 28 post-randomization for subjects with cIAI and (c) the composite clinical and microbiological response at the early follow-up visit, EFU (Day 5 to 9 following completion of therapy) for subjects with cUTI. In addition, the difference between Treatment Group 1 (IMI/REL) and Treatment Group 2 (CMS + IMI) will be estimated along with a 90% confidence interval. The within-group 95% confidence intervals will be calculated using the Agresti & Coull method. The between-group 90% confidence interval will be calculated using the Miettinen and Nurminen method [78].

Key secondary efficacy objectives of the study are to estimate: 1) the proportion of subjects with a favorable clinical response within each of Treatment Group 1 (IMI/REL) and Treatment Group 2 (CMS + IMI) at Day 28 post-randomization, and 2) the incidence of all-cause mortality through Day 28 post-randomization in Treatment Group 1 (IMI/REL) and in Treatment Group 2 (CMS + IMI). In addition, the difference between Treatment Group 1 (IMI/REL) and Treatment Group 2 (CMS + IMI) will be estimated along with the 90% confidence interval for these key secondary endpoints.

IV study therapy will be administered for a minimum of either 5 (cIAI and cUTI) or 7 (HABP/VABP) days up to a maximum of 21 days, unless a longer duration is approved by the Sponsor (see Section 7.1.2.1). The duration of therapy will be summarized by treatment group for the overall population as well as by infection site. In addition, the impact of any difference in duration of therapy on the treatment group comparisons will be assessed.

The primary and key secondary endpoints, primary analysis population, and statistical methods that will be employed for the efficacy analyses are presented in [Table 16](#). The mMITT population will serve as the primary population for efficacy analyses in this study.

8.1.2 Safety Analysis

The All-Subjects-as-Treated (ASaT) population will be employed for safety analyses. The ASaT population consists of all subjects who received at least one dose of IV study therapy. The ASaT includes non-randomized subjects in Treatment Group 3 (IMI/REL), as well as randomized subjects in Treatment Group 1 (IMI/REL) and Treatment Group 2 (CMS + IMI).

Any safety analysis that involves a comparison of IMI/REL to CMS + IMI will be based on Treatment Group 1 and Treatment Group 2 (the randomized treatment groups). Safety for Treatment Group 3 (the non-randomized treatment group) will be summarized separately using descriptive statistics.

A stated key secondary safety objective of the study is to estimate the proportion of subjects who experience treatment-emergent nephrotoxicity in Treatment Group 1 (IMI/REL) and in Treatment Group 2 (CMS + IMI). The incidence of treatment-emergent nephrotoxicity will be compared between Treatment Group 1 (IMI/REL) and Treatment Group 2 (CMS + IMI).

Table 16 Summary of Analysis Strategy for Primary and Key Secondary Endpoints

Endpoint/Variable (Description, Timepoint)	Statistical Method	Analysis Population	Missing Data Approach
Primary:			
Proportion of subjects with an favorable overall response	95% confidence interval (Agresti & Coull) for single group proportion	mMITT ^a	Missing = Failure
Key Secondary:			
Proportion of subjects with favorable clinical response at Day 28 post randomization	95% confidence interval (Agresti & Coull) for single group proportion	mMITT ^a	Missing = Failure
Proportion of subjects with all-cause mortality at Day 28 post randomization	95% confidence interval (Agresti & Coull) for single group proportion	mMITT ^a	Missing = Failure
Proportion of subjects who experience treatment-emergent nephrotoxicity	95% confidence interval (Agresti & Coull) for single group proportion and Fisher Exact Test	ASaT ^a	Data as Observed

^a The mMITT population is defined as all randomized subjects who receive at least one dose of each study drug within a given IV study therapy regimen, and who have a baseline bacterial pathogen meeting inclusion criterion #3; in the case of a polymicrobial infection, at least one pathogen must satisfy the requirements of inclusion criterion #3, and all pathogens identified at the baseline time point must be susceptible to both IMI/REL and colistin. The ASaT population consists of all subjects who received at least one dose of IV study therapy.

8.1.3 Power and Sample Size

This study will randomize approximately 54 subjects in a 2:1 ratio into 2 treatment groups (Group 1: IMI/REL and Group 2: CMS + IMI) in order to obtain a minimum of 45 subjects (15 per infection type) who meet the criteria for inclusion in the microbiological modified intent-to-treat (mMITT) population. An additional 5 to 10 subjects with imipenem-resistant and colistin-resistant bacterial infection will be enrolled into a third non-randomized, open-label treatment group (Group 3: IMI/REL). This is an estimation study; no formal statistical testing will be performed for the efficacy endpoints. The sample sizes planned for the study arise from logistic feasibility and are not driven by statistical considerations.

8.2 Statistical Analysis Plan

8.2.1 Responsibility for Analyses/In-House Blinding

The statistical analyses of the data obtained from this study will be the responsibility of the Clinical Biostatistics department of the Sponsor. Certain specific analyses such as PK and the evaluation of PK/PD association will be the responsibility of the appropriate departments of the Sponsor.

Separate functional unblinding for bioanalysis will be conducted in support of PK evaluations. A small team as specified in a separate Modeling and Simulation (M&S) Modeling Analysis Plan, and who are separate from the study team, will be unblinded for the

purpose of preparing the PK analyses. No interim data or results will be shared with the study team before the primary analyses have been completed, and the unblinded group will not be members of the study team. No decisions are made based on this functional unblinding that will influence the conduct of the trial.

This study will be conducted as a double-blind study under in-house blinding procedures (except for Treatment group 3). The official, final database will not be unblinded until medical/scientific review has been performed, protocol violators have been identified, and data have been declared final and complete.

The Clinical Biostatistics department will generate the randomized allocation schedule(s) for study treatment assignment. Randomization will be implemented in IVRS.

8.2.2 Hypotheses/Estimation

Objectives and hypotheses of the study are stated in Section 3.

8.2.3 Analysis Endpoints

Efficacy and safety endpoints that will be evaluated are listed below.

8.2.3.1 Efficacy Endpoints

A full description of the efficacy measures is provided in Section 4.2.3.1. The primary efficacy endpoint is the proportion of subjects with a favorable overall response as assessed for each of the three infection types. Key secondary endpoints are: 1) the proportion of subjects with a favorable clinical response at 28 days following initiation of IV study therapy and 2) the incidence of all-cause mortality within 28 days after initiation of study therapy.

Other secondary endpoints include: 1) the proportion of subjects with a favorable clinical response at the OTX, EOT and EFU timepoints, 2) the proportion of subjects with a favorable microbiological response at the OTX, EOT and EFU timepoints, and 3) the proportion of subjects with favorable overall response for each infection type.

The duration of IV study therapy will be summarized by treatment group for each of the infection types. The proportion of subjects with favorable clinical and microbiological response will be assessed separately for each pathogen identified at baseline as exploratory endpoints.

The proportion of subjects with a favorable clinical response at all endpoint visits and a favorable microbiological response (cUTI) at OTX, EOT and EFU will be summarized for Treatment Group 3 subjects as exploratory efficacy endpoints.

8.2.3.2 Safety Endpoints

A description of safety measures is provided in Section 4.2.3.2.

The proportion of subjects who experience treatment-emergent nephrotoxicity will be summarized by treatment group. In addition, Treatment Group 1 (IMI/REL) and Treatment Group 2 (CMS + IMI) will be compared with respect to the incidence of treatment-emergent nephrotoxicity.

The rest of the safety analysis will follow a tiered approach and will use only data from the randomized treatment groups: Treatment Group 1 (IMI/REL) and Treatment Group 2 (CMS + IMI). The tiers differ with respect to the analyses that will be performed. Safety parameters or adverse experiences of special interest that are identified *a priori* constitute “Tier 1” safety endpoints that will be subject to inferential testing for statistical significance with p-values and 95% confidence intervals provided for between-group comparisons. Other safety parameters will be considered Tier 2 or Tier 3. Tier 2 parameters (requires that at least 4 subjects in at least one treatment group exhibit the event) will be assessed via point estimates with 95% confidence intervals provided for between-group comparisons; only point estimates by treatment group are provided for Tier 3 safety parameters.

For this protocol, the following are pre-specified events of interest (Tier 1 events).

1. Treatment-emergent nephrotoxicity as defined in [Table 9](#).
2. An elevated AST or ALT laboratory value that is greater than or equal to 3 X ULN and an elevated total bilirubin laboratory value that is greater than or equal to 2 X ULN and, at the same time, an alkaline phosphatase laboratory value that is less than 2 X ULN, as a result of within-protocol-specific testing or unscheduled testing.
3. A confirmed (i.e., verified by repeat testing) elevated AST or ALT laboratory value that is greater than or equal to 5 X ULN as a result of within-protocol-specific testing or unscheduled testing.

The broad clinical and laboratory adverse experience (AE) categories, consisting of the percentage of subjects with any AE, a drug-related AE, a serious AE, an AE which is both drug related and serious, who discontinued IV study therapy due to an AE, and who discontinued IV study therapy due to a drug-related AE, will be considered Tier 2 endpoints. Please refer to Section 8.2.5.2 for further details regarding these safety endpoints and their analyses.

8.2.4 Analysis Populations

8.2.4.1 Efficacy Analysis Populations

The microbiological modified Intention to Treat (mMITT) population will serve as the primary population for efficacy analyses in this study. The mMITT population is defined as all randomized subjects who receive at least one dose of each study drug within a given IV study therapy regimen, and who have a baseline bacterial pathogen meeting inclusion criterion #3. In the case of a polymicrobial infection, at least one pathogen must satisfy the requirements of inclusion criterion #3, and all pathogens identified at the baseline time point must be susceptible to both IMI/REL and colistin. Subjects will be included in the treatment group to which they are randomized for the analysis of efficacy data using the mMITT population.

The per-protocol (PP) population will serve as the secondary population for the primary efficacy endpoint (proportion of subjects with a favorable overall response as assessed for each of the three infection types). The PP population is a subset of the mMITT population who also meet the following criteria:

1. Meet important diagnostic criteria for entry into the study,

2. Have no significant deviation from the protocol that could impact the assessment of efficacy, and
3. Receive the minimum duration of IV study therapy as detailed in Section 5.2

The final exclusion criteria and list of patients who will be excluded from the PP population will be documented prior to unblinding.

Details on the approach to handling missing data are provided in Section 8.2.5 (Statistical Methods).

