Colistin is available for intravenous administration as CMS, an inactive prodrug. After parenteral administration, CMS is metabolized to colistin. Colistin acts by binding phospholipids in the outer membrane of Gram-negative bacteria, causing cell wall destabilization and cell death. Colistin is active against many resistant Gram-negative bacteria, including *P. aeruginosa*, *Acinetobacter baumannii*, *K. pneumoniae*, and *Escherichia coli* [18]. Activity against other bacterial isolates, such as *Haemophilus influenzae*, *Salmonella* species (spp.), *Shigella* spp., *Legionella pneumophila*, *Aeromonas* spp., *Citrobacter* spp. and *Bordetella pertussis*, has also been reported [18]. Colistin is not active against *Proteus* spp., *Providencia* spp., *Burkholderia cepacia*, *Brucella* spp., *Edwardsiella* spp. or *Serratia* spp. [18, 19]. Gram-negative and Gram-positive aerobic cocci, Gram-positive aerobic bacilli, and all anaerobes are resistant to colistin [19]. Colistin is currently used in clinical situations such as in critically ill patients with CR Gram-negative infections. Successful treatment outcomes have been documented for various infections, including UTI, IAI, and bronchial and lower respiratory tract infections, including both HABP and VABP [11-13, 20-28].

IMI, a potent broad spectrum β -lactam antibacterial agent from the carbapenem class, has been used clinically for the treatment of serious infections since 1985. The bactericidal activity of imipenem results from inhibition of cell wall synthesis. Imipenem, when administered alone, is metabolized in the kidneys by dehydropeptidase I, resulting in relatively low levels in the urine. Cilastatin (CIL) sodium is an inhibitor of this enzyme and effectively prevents renal metabolism of imipenem so that, when given together, full adequate antibacterial levels of imipenem are achieved. According to the approved package circular, IMI is active against a broad range of Gram-positive and Gram-negative organisms and is approved for use in a variety of infections, including lower respiratory tract infections, urinary tract infections (complicated and uncomplicated), intra-abdominal infections, gynecologic infections, bacterial septicemia, bone and joint infections, skin and skin structure infections, endocarditis, and polymicrobial infections.

The rationale for using colistin (CMS) + IMI as the comparator in this study is provided in Section 4.2.2.6.

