5.1.2 Subject Inclusion Criteria

5.1.2.1 Treatment Groups 1 and 2

In order to be eligible for participation in this trial, the subject must:

1. be ≥ 18 years of age on the day of signing informed consent at the randomization visit.

NOTE: Adults are the intended study population for this protocol. Subjects under the age of legal consent per a specific country's regulations should be excluded from participation in this study

2. require hospitalization and treatment with IV antibiotic therapy for a new, persistent (defined as inadequate response to current therapy or failure to improve as expected) or progressing (defined as clinically worsening despite treatment) bacterial infection with at least one of the following primary infection types:
 - Hospital-acquired bacterial pneumonia (HABP) or ventilator-associated bacterial pneumonia (VABP)
 - Complicated intra-abdominal infection (cIAI)
 - Complicated urinary tract infection (cUTI)

NOTE: Diagnostic criteria, including relevant radiographic, clinical and microbiological evidence, for each infection type are in Appendix 12.5.

3. has positive culture data obtained from the primary infection-site specimen collected within 1 week of study entry and at least one of the suspected causative pathogen(s) from that specimen meets all of the following criteria:
 - a. has been identified as a Gram-negative bacterium, AND
 - b. has culture-confirmed imipenem resistance (MIC of isolate is above the imipenem-susceptible breakpoint) based on panels provided by the Sponsor, AND
 - c. has culture-confirmed susceptibility to colistin (MIC of isolate is at or below the colistin-susceptible breakpoint) and to IMI/REL (MIC of isolate is at or below the imipenem-susceptible breakpoint) based on panels provided by the Sponsor.

4. agree to allow any bacterial isolates obtained from protocol-required specimens related to the current infection to be provided the Central Microbiology Reference Laboratory for study-related microbiological testing, long-term storage, and other future testing.

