5.5 Concomitant Medications/Vaccinations (allowed & prohibited)

Medications or vaccinations specifically prohibited in the exclusion criteria are not allowed during the ongoing trial. Listed below are some specific restrictions for concomitant therapy or vaccination during the course of the trial. If there is a clinical indication for one of these or other medications or vaccinations specifically prohibited during the trial, discontinuation from trial therapy or vaccination may be required. The investigator should discuss any questions regarding this with the Sponsor Clinical Director. The final decision on any supportive therapy or vaccination rests with the investigator and/or the subject's primary physician. However, the decision to continue the subject on trial therapy or vaccination schedule requires the mutual agreement of the investigator, the Sponsor and the subject.

NOTE: With the exception of >24 hours of colistin for subjects in Treatment Groups 1 and 2 (see Section 5.1.3.1, Criterion #4) there are no restrictions to prior antimicrobial therapy.

The following concomitant medications/therapies are NOT permitted in this study:

1. Valproic acid/divalproex sodium
2. Non-study IV, oral, or inhaled antibacterial treatments with known coverage of Gram-negative bacteria of interest (i.e., Enterobacteriaceae, *Pseudomonas* spp. and Gram-negative anaerobic bacilli).

Importantly, the following antibacterial medications are permitted:

- a. IV vancomycin, IV daptomycin, or IV linezolid to treat confirmed or suspected MRSA infection. If added, IV vancomycin, daptomycin, or linezolid should be used according to the investigator's usual practice. Daptomycin is not indicated for the treatment of HABP/VABP.

- b. IV linezolid or IV daptomycin to treat confirmed or suspected VRE infection. If added, linezolid or daptomycin should be used according to the investigator's usual practice. Daptomycin should not be used to treat HABP/VABP.
 - c. TMP/SMX or other standard-of-care agent for prophylaxis of opportunistic infection (e.g., *P. jiroveci* infection) in immunocompromised subjects.
3. Use of systemic antifungal therapy for disseminated fungal infection, fungemia, or for pulmonary infection in HABP/VABP subjects.

Antifungal medications are permitted in the following clinical situations:

- a. Antifungal medications for treatment of mucocutaneous infection (e.g., vaginal candidiasis, onychomycosis).

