- b. Antifungal medications for prophylaxis of invasive fungal infections, such as in immunocompromised patients.
- c. Antifungal medications for treatment of fungal pathogens isolated in polymicrobial cIAI, if treatment of isolated fungal pathogens is required.

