7.1.3.2 Culture and Susceptibility Testing

Culture (aerobic for all infection-site specimens and anaerobic for cIAI specimens) and *in vitro* susceptibility testing of infection site specimens collected within 1 week prior to study entry as well as specimens collected at the study-specified time points (see Section 6.0, Trial Flow Chart) will be performed. The local laboratory for each site will be provided with panels to determine *in vitro* susceptibility for IMI, IMI/REL and colistin according to procedures specified by the Sponsor in a separate laboratory manual. Other susceptibility testing for medical management should be performed by the site's local laboratory per each laboratory's standard procedures. In addition to local laboratory testing, all Gram-negative pathogens obtained from infection-site specimens collected from randomized subjects will be retained by the local clinical microbiology laboratory and sent to the central microbiology reference laboratory. Additional details regarding bacterial specimen collection, processing, handling, and shipment will be provided by the Sponsor in a separate microbiology laboratory manual.

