7.1.3.2.1 Prior Infection-Site Specimens

In order to be considered eligible for participation in PN013, identification and *in vitro* susceptibility of infection-site pathogens from samples collected within 1 week prior to study entry must be determined. Specifically, for randomized as well as open-label, nonrandomized subjects, the culture-associated criteria (Inclusion Criterion #3) described in Section 5.1.2.1 and 5.1.2.2, respectively, must be confirmed. In order to avoid potential delay in receipt of effective therapy for study subjects, the local laboratory for each site will be provided with panels to determine *in vitro* susceptibility (to IMI, IMI/REL and colistin) of Gram-negative bacterial isolates obtained from specimen types of interest as part of routine standard-of-care testing at the institution. Local laboratories will include the Sponsor-provided susceptibility panels in parallel with routine, first-line susceptibility testing of specified Gram-negative bacterial isolates scheduled for *in vitro* susceptibility testing per routine standard-of-care by the site's local laboratory (a separate microbiology laboratory manual will be provided for the Sponsor panels). Since subjects cannot be randomized until supportive culture and *in-vitro* susceptibility data are confirmed, information obtained from this routine testing will allow for rapid eligibility evaluation. In this way, subjects can be randomized without delay incurred due to specimen collection and subsequent culture and susceptibility testing. This will also allow for enrollment of subjects who may not otherwise be eligible as a consequence of inability to collect baseline cultures (e.g., cIAI in whom prior sample was obtained perioperatively).

Once a subject is randomized into the study and consent is obtained, all Gram-negative pathogen(s) isolated from the specimen obtained for pre-screening must be submitted to the central microbiology laboratory. Culture and susceptibility data associated with pre-screening will also be recorded on the appropriate eCRFs. Bacterial isolates and related data will not be provided to the Sponsor unless consent is obtained from the study subject at the time of entry.

Additional details regarding bacterial specimen processing, handling, and shipment will be provided by the Sponsor in a separate microbiology laboratory manual.

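### As written, the mMITT clause on polymicrobial infection drops eligible subjects who have a Gram-positive or anaerobic co-pathogen, and the cIAI stratum is the most exposed

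*Combined protocol and SAP*

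**What the plan says.** Inclusion criterion #3 (section 5.1.2.1) asks only that "at least one of the suspected causative pathogen(s) from that specimen meets all of the following criteria", namely Gram-negative, imipenem-resistant, and susceptible to colistin and to IMI/REL. A polymicrobial infection is admissible if one organism qualifies.

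The mMITT definition goes further. For polymicrobial infection it adds that "all pathogens identified at the baseline time point must be susceptible to both IMI/REL and colistin" (section 8.2.4.1, with the same condition in 8.1.1 and Table 16 footnote a).

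On colistin's spectrum, section 4.1.3 says: "Gram-negative and Gram-positive aerobic cocci, Gram-positive aerobic bacilli, and all anaerobes are resistant to colistin".

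Co-pathogens of these kinds are foreseen. Section 7.1.3.2 specifies "Culture (aerobic for all infection-site specimens and anaerobic for cIAI specimens". Section 5.5 permits "IV vancomycin, IV daptomycin, or IV linezolid to treat confirmed or suspected MRSA infection", has a parallel allowance for VRE, and permits "Antifungal medications for treatment of fungal pathogens isolated in polymicrobial cIAI". Appendix 12.5 lists intestinal perforation with abscess or fecal contamination among the qualifying cIAI diagnoses.

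The per-protocol population is a subset of mMITT. The plan randomises about 18 subjects per infection type, 2:1, to obtain at least 15 mMITT subjects in each (54 and 45 overall).

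**The concern.** Entry and analysis apply different tests to the same culture result. Entry asks about one pathogen; the primary population asks about all of them and measures each against colistin alone. Yet the comparator is colistin plus imipenem, and section 4.2.2.6 credits imipenem with broad cover that includes Gram-positive organisms and anaerobes. Both arms receive it. The clause therefore removes subjects because of an organism that colistin was never expected to cover.

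Two things are at stake. The first is who the primary estimate describes: under the literal rule, the cIAI result applies only to infections whose every pathogen is colistin-susceptible. Because the per-protocol set lies inside mMITT, neither named efficacy population recovers the excluded subjects. The second is the mMITT yield in a stratum planned to lose no more than 3 of 18.

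**Working it through.** **Step 1: do the passages combine as claimed?**

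- A subject with a qualifying Gram-negative pathogen plus an anaerobe or Gram-positive pathogen meets inclusion criterion #3.
- By section 4.1.3 the second organism is colistin-resistant.
- By section 8.2.4.1 the subject then fails the all-pathogens condition and leaves mMITT.

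This follows from the text and needs no assumed rate.

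**Step 2: what loss does the plan allow?** No mMITT exclusion rate is stated, so 54 cannot be derived from inputs. Working back, 1 − 45/54 = 1 − 15/18 = 16.7%, for all causes together. The pooled and per-stratum figures agree with each other.

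**Step 3: yield over assumed exclusion rates.** Let q be the share of randomised cIAI subjects excluded from mMITT for any reason. The values of q are assumptions. With independent subjects and enrolment stopped at 18, the number retained is Binomial(18, 1 − q). The expected yield is 18(1 − q), and the number to randomise for an expected 15 is 15/(1 − q), rounded up. The pooled columns add two further strata of 18, with either no loss or 10% loss in each.

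| q (cIAI) | Expected cIAI mMITT | P(at least 15 of 18) | cIAI subjects to randomise | P(total at least 45), no loss elsewhere | P(total at least 45), 10% loss elsewhere |
|---|---|---|---|---|---|
| 10% | 16.2 | 0.90 | 17 | above 0.99 | 0.96 |
| 16.7% | 15.0 | 0.65 | 18 | above 0.99 | 0.88 |
| 20% | 14.4 | 0.50 | 19 | above 0.99 | 0.83 |
| 30% | 12.6 | 0.16 | 22 | 0.98 | 0.59 |
| 40% | 10.8 | 0.03 | 25 | 0.87 | 0.33 |
| 50% | 9.0 | 0.004 | 30 | 0.59 | 0.13 |
| 60% | 7.2 | 0.0002 | 38 | 0.26 | 0.03 |

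The probability of reaching 15 in cIAI crosses one half at q = 20.0%. The pooled 45 becomes less likely than not only when q is above 50% with no loss elsewhere, or somewhere between 30% and 40% with 10% loss in each other stratum.

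**Step 4: the comparator cell.** At 2:1, 18 randomised cIAI subjects give 6 on CMS + IMI. Section 8.2.8 reports a between-group subgroup difference only with at least 4 subjects in each group. The chance of keeping at least 4 of 6 is:

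- q = 30%: 15(0.7⁴)(0.3²) + 6(0.7⁵)(0.3) + 0.7⁶ = 0.324 + 0.303 + 0.118 = 0.74.
- q = 50%: (15 + 6 + 1)/64 = 0.34.

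Unless the stratum is extended, the cIAI between-group interval may not be reportable.

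**The case against.** The best defence is that only Gram-negatives were meant. Criterion #3 concerns a Gram-negative organism, the qualifying pathogen for microbiological response is Gram-negative, and section 7.1.3.2.1 supplies panels for susceptibility ("to IMI, IMI/REL and colistin) of Gram-negative bacterial isolates"), with no stated colistin test for other organisms. That intent is plausible, but the clause does not carry the limit in any of its three places, although the plan writes Gram-negative elsewhere when it means it. The two readings give different primary populations.

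Three further points stand in part.

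- The clause speaks of pathogens, not every organism grown, and MRSA or VRE drugs may be given on suspicion. Losses could be smaller than a count of co-isolates would suggest.
- Sections 2.1 and 5.4 let the Sponsor enrol beyond 54 and keep strata open until each has 15 mMITT subjects. If used, this protects the numbers at the cost of time and further subjects. It does not bring back the excluded kind of infection.
- This is an estimation study without efficacy testing, and membership depends on baseline cultures. Nothing here implies unequal exclusion between arms.

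A reader might infer that the 45-subject target is unlikely to be met from 54. The documents do not support that: no co-pathogen rate is given, and even at 30% cIAI loss with none elsewhere the expected total is 12.6 + 18 + 18 = 48.6.

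A reader might also infer that subjects with an imipenem-susceptible, colistin-resistant Gram-negative co-pathogen are wrongly excluded. Section 4.2.2.3 says imipenem is not the primary treatment modality in the comparator arm, so requiring colistin susceptibility of Gram-negative pathogens is a defensible choice.

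**Conclusion.** The point holds as a defect in the definition of the primary population. Followed literally, the clause excludes eligible, treated subjects because of Gram-positive or anaerobic co-pathogens that the protocol itself calls colistin-resistant. That conclusion rests on the text alone.

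The numerical effect is conditional. It depends on an unstated cIAI exclusion rate, on independence between subjects, and on enrolment stopping at 18. Above about 20% exclusion, the 15-per-stratum requirement in cIAI would more likely than not be missed; the pooled 45 tolerates considerably more. That the cIAI stratum will in fact be depleted cannot be concluded from these documents. The narrowing of what the cIAI estimate describes remains however many subjects are added.

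**What to change.** Before unblinding, amend sections 8.1.1 and 8.2.4.1 and Table 16 footnote a so that the all-pathogens condition applies to aerobic Gram-negative baseline pathogens only, and say that Gram-positive, anaerobic and fungal co-pathogens do not affect mMITT membership. The word aerobic is needed: exclusion criterion 10 (section 5.1.3.1) recognises Gram-negative anaerobic bacilli, and section 4.1.3 makes all anaerobes colistin-resistant. Keep the present rule as a sensitivity population for the primary endpoint, and state the mMITT exclusion rate assumed for cIAI.

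The cost is wording in three places and one extra table, with no new data or subjects. The drawback is that the primary set would include some subjects with co-pathogens not covered by study drug, such as MRSA or VRE, for which section 5.5 permits concomitant therapy. The sensitivity population shows how much that matters.
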